**Table 11-1: Clinical laboratory measurements**

Category	Panel	Variable
Hematology	Red blood cell	RBC count, hemoglobin, hematocrit
	Red blood cell indices	MCH, MCHC, MCV
	Platelet	Platelets

**Table 11–1: Clinical laboratory measurements**

Category	Panel	Variable
	White blood cell	WBC count
	White blood cell differential	Absolute counts: ANC, basophils, eosinophils, ALC, monocytes, atypical lymphocytes (if indicated) Percentages: neutrophils/leukocytes, basophils/leukocytes, eosinophils/leukocytes, lymphocytes/leukocytes, monocytes/leukocytes
Chemistry	Electrolytes	Sodium, chloride, potassium, calcium, magnesium
	Kidney function	BUN, creatinine
	Liver function	AST, ALT, GGT, ALP, LDH, total bilirubin (direct bilirubin, indirect bilirubin, if indicated)
	Lipids	Total cholesterol
	Metabolic function	Glucose
	Hormones	FSH b
	Fertility	Pregnancy test a
	Other	CRP
Urinalysis	Dipstick	pH, protein, blood, leukocyte esterase, nitrite, glucose
	Urine sediment (if indicated)	WBC, RBC, epithelial cells (squamous, transitional and renal tubular), hyaline casts, WBC casts, RBC casts, waxy casts, granular casts, calcium oxalate crystals, uric acid crystals, triphosphate crystals, yeast, bacteria, amorphous urates, amorphous phosphates

ALC=absolute lymphocyte count; ALP=alkaline phosphatase; ALT=alanine aminotransferase; ANC=absolute neutrophil count; AST=aspartate aminotransferase; BUN=blood urea nitrogen; CRP=C-reactive protein; FSH=follicle stimulating hormone; GGT=gamma glutamyltransferase; LDH=lactate dehydrogenase; MCH=mean corpuscular hemoglobin; MCHC=mean corpuscular hemoglobin concentration; MCV=mean corpuscular volume; RBC=red blood cell; WBC=white blood cell

a Pregnancy testing will consist of serum testing at the SFU Visit. The pregnancy test will be urine at all other visits and will be performed locally.

b The FSH test should only be performed on postmenopausal females who have been postmenopausal for ≥1 year and last menstrual cycle occurred <2 years ago.

## 11.4 Vital signs, physical findings, and other observations related to safety

### 11.4.1 Vital signs

Vital signs will be measured at every visit and will include:

- Systolic and diastolic blood pressure
- Pulse rate
- Body temperature (oral, axillary, or otic)

Vital signs are to be measured prior to blood sampling, and prior to dosing, where applicable.

A by-subject listing of all vital sign measurements and changes from Baseline will be presented by PS0016 randomized treatment group and visit. The listing will include a flag for measurements identified as TEMA/potentially clinically significant (PCS) as calculated by the criteria outlined in [Table 14-4](#).

Descriptive statistics will be reported for all vital sign measurements. Measured values and changes from Baseline will be summarized by vital signs variable and visit for each PS0016 randomized treatment group.

The number and percentage of subjects with TEMA/PCS vital sign values will be summarized by PS0016 randomized treatment group and variable at each visit and overall (ie across all PS0018 visits).

#### **11.4.2 Body weight**

A by-subject listing of body weight will be presented. No summary tabulations will be provided for this variable.

#### **11.4.3 12-Lead Electrocardiograms**

Standard 12-lead ECG will be recorded after 10 minutes of rest in the supine or semi recumbent position. The following ECG variables will be recorded together with the Investigator's interpretation of the ECG profile:

- Heart rate
- PR interval
- QRS duration
- QT interval
- QT corrected for heart rate using Fridericia's formula (QTcF)

The results of all ECG variables will be reported in the by-subject listings. The listing will also include the change from Baseline for numeric parameters and will be presented by PS0016 randomized treatment group and visit.

Measured values and changes from Baseline will be summarized for each variable by PS0016 randomized treatment group and visit.

The following cut-points in QTcF (raw data and change from Baseline) will be summarized categorically by PS0016 randomized treatment group (number and percentage of subjects) and visit. The denominator for the percentages will be the number of subjects with a non-missing measurement for the variable at the specific visit.

Raw QTcF data:

- <450msec
- ≥450 msec to <480msec
- ≥480msec to <500msec
- ≥500msec

Change from Baseline QTcF:

- <30msec
- $\geq 30$ msec to <60msec
- $\geq 60$ msec

Electrocardiogram findings will be listed separately.

#### **11.4.4 Other safety variables**

##### **11.4.4.1 Physical examination**

Physical examination will not be reported as part of the CSR.

##### **11.4.4.2 Tuberculosis**

#### **Tuberculosis assessment by interferon gamma release assay**

The TB assessment by interferon gamma release assay will be performed for all subjects. The test results will be listed for each subject by PS0016 randomized treatment group and visit, reported as positive, negative, or indeterminate.

#### **Chest x ray for Tuberculosis**

Chest x ray will be performed in PS0018 only when required to confirm or exclude TB. Any clinically significant findings on chest x ray will be documented in the eCRF as an AE and will thus be listed and summarized together with TEAEs as described in [Section 11.2.3](#).

#### **Tuberculosis questionnaire**

The TB questionnaire results will be listed for each subject by PS0016 randomized treatment group and visit.

##### **11.4.4.3 Columbia-Suicide Severity Rating Scale**

The results of the C-SSRS will be listed for each subject by PS0016 randomized treatment group and visit.

## **12 OTHER ANALYSES**

A listing of comments on the SS will be presented, if applicable.

## 14 APPENDICES

### 14.1 Classification of markedly abnormal laboratory values based on CTCAE grades

The criteria for assessing laboratory values as markedly abnormal are presented in [Table 14–2](#). Baseline in the table refers to PS0016 Baseline.

**Table 14–2: Criteria for markedly abnormal laboratory tests**

Category	Panel	Variable	Criteria (CTCAE Grade 3 and above)	
Hematology	Red blood cell	Hemoglobin (Decrease)	<80 g/L	
		Hemoglobin (Increase)	>4 g/dL (>40 g/L) above ULN OR >4 g/dL (>40 g/L) above Baseline if Baseline is >ULN	
	White blood cell	WBC count (Decrease)	<2.0 x 10  /L	
		WBC count (Increase)	>100 x 10  /L	
	White blood cell differential	ALC (Decrease)	<0.5 x 10  /L	
		ALC (Increase)	>20 x 10  /L	
		ANC	<1.0 x 10  /L	
		Platelet	Platelet	<50 x 10  /L
	Chemistry	Liver function	ALT	>5.0 x ULN
			ALP	>5.0 x ULN
AST			>5.0 x ULN	
Total bilirubin			>3.0 x ULN	
GGT			>5.0 x ULN	
		Kidney function	Creatinine	>3.0 x Baseline value OR >3.0 x ULN
Electrolytes		Calcium (Decrease)	<1.75 mmol/L	
		Calcium (Increase)	>3.1 mmol/L	
		Magnesium (Increase)	<0.4 mmol/L	
		Magnesium (Increase)	>1.23 mmol/L	
	Potassium (Decrease)	<3.0 mmol/L		
	Potassium (Increase)	>6.0 mmol/L		
	Sodium (Decrease)	<130 mmol/L		
Sodium (Increase)	>155 mmol/L			

**Table 14–2: Criteria for markedly abnormal laboratory tests**

Category	Panel	Variable	Criteria (CTCAE Grade 3 and above)
	Lipids	Total cholesterol	>10.34 mmol/L

ALC= absolute lymphocyte count; ALP=alkaline phosphatase; ALT=alanine aminotransferase; ANC= absolute neutrophil count; AST=aspartate aminotransferase; GGT=gamma glutamyltransferase; RBC=red blood cell; ULN=upper limit of normal, WBC=white blood cell:

## 14.2 Treatment-emergent abnormal liver values

The criteria for identifying treatment-emergent liver function abnormalities are presented in Table 14–3. Subjects will be counted in all applicable categories for the tabulations ie, a subject with  $\geq 5$  x ULN in aspartate aminotransferase (AST) will also be counted in the  $\geq 3$  x ULN in AST category, the  $\geq 3$  x ULN in AST or alanine aminotransferase (ALT) category and the  $\geq 5$  x ULN in AST or ALT category. Increases from Baseline are based on PS0016 Baseline.

**Table 14–3: Definition of treatment emergent liver function values**

Criterion
$\geq 3$ x ULN increase for AST
$\geq 5$ x ULN increase for AST
$\geq 10$ x ULN increase for AST
$\geq 20$ x ULN increase for AST
$\geq 3$ x ULN increase for ALT
$\geq 5$ x ULN increase for ALT
$\geq 10$ x ULN increase for ALT
$\geq 20$ x ULN increase for ALT
$\geq 3$ x ULN increase for AST or ALT
$\geq 5$ x ULN increase for AST or ALT
$\geq 10$ x ULN increase for AST or ALT
$\geq 20$ x ULN increase for AST or ALT
$\geq 1$ x ULN increase for bilirubin
$\geq 1.5$ x ULN increase for bilirubin
$\geq 1.5$ x ULN increase for ALP
$\geq 1$ x ULN increase for bilirubin and 3 x ULN increase of either AST or ALT (at the same visit)
$\geq 2$ x ULN increase for bilirubin and 3 x ULN increase of either AST or ALT (at the same visit)

ALP=alkaline phosphatase; ALT=alanine aminotransferase; AST=aspartate aminotransferase; ULN=upper limit of normal.

### 14.3 Adverse events of special monitoring

The following AESM are defined for bimekizumab and will be summarized separately as described in [Section 11.2.3](#):

- Major cardiovascular events
- Serious infections, including opportunistic infections and tuberculosis (TB)
- Malignancies including lymphoma
- Cytopenias
- Neuropsychiatric events (in particular, depression and suicide)
- Inflammatory bowel disease
- Anaphylactic reaction (hypersensitivity and anaphylactic reactions)
- Hepatic events and drug-induced liver injury

All AESM tabulations will be presented by Treatment at onset, SOC, HLT and PT, based on the SS, and will include the EAIR and EAER in the 'Any TEAE' categories only.

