### 9.6 Adverse events for special monitoring

UCB has identified AEs for special monitoring (AESM). An AESM is an AE or safety topic for which special monitoring, additional data collection activities, and/or enhanced signal detection activities (within UCB), are considered appropriate. Identified AESM can be of particular interest based on findings from the IMP clinical program to date, potential risks generally associated with biologic immunomodulators, or comorbidities and risk factors prevalent in the study population.

Adverse events for special monitoring for this study include: serious infections (including opportunistic infections and TB; see [Section 9.8.1](#)), cytopenias, hypersensitivities, suicide ideation or behavior (assessed using the C-SSRS; see [Section 9.8.6](#)), depression and anxiety (assessed using the HADS; see [Section 12.4](#)), major cardiovascular events, and liver function test changes/enzyme elevations (ALT, AST, bilirubin; see [Section 9.7.1](#)), malignancies, and inflammatory bowel diseases.

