### 11.2.3 Presentation of adverse events

An overview of the number and percentage of subjects who experience TEAEs will be presented based on the SS. This tabulation will include the number and percentage of subjects with any TEAEs, serious TEAEs, related TEAEs, discontinuation due to TEAEs, severe TEAEs, AEs leading to death and TEAEs leading to death; event counts will also be included.

- The tabulation will be presented by PS0018 dose at onset.
- This tabulation will be repeated by Dose adjustment and PS0016 randomized treatment group.

In addition, the following summaries will be presented by PS0018 dose at onset, SOC, high level term (HLT) and PT, based on the SS:

- Incidence of TEAEs by PS0018 dose at onset, including the EAIR and EAER calculated as described in [Section 11.2.2](#) for the 'Any TEAE' category only
- Incidence of TEAEs by PS0018 dose at onset, including the EAIR and EAER calculated as described in [Section 11.2.2](#) for the 'Any TEAE' category only by overall ADA status (positive/negative)
- Incidence of TEAEs by Dose adjustment and PS0016 randomized treatment group
- Incidence of serious TEAEs by PS0018 dose at onset and Dose adjustment
- Incidence of TEAEs by relationship and PS0018 dose at onset
- Incidence of TEAEs by maximum relationship and PS0018 dose at onset
- Incidence of TEAEs by maximum intensity and PS0018 dose at onset
- Incidence of fatal TEAEs by relationship and PS0018 dose at onset

- Incidence of serious TEAEs by relationship and PS0018 dose at onset
- Incidence of non-serious TEAEs above threshold of 5% of subjects by PS0018 dose at onset
- Incidence of non-serious TEAEs above threshold of 5% of subjects by relationship and PS0018 dose at onset
- Incidence of ongoing AEs from PS0016
- Incidence of ongoing AEs from PS0016 which do not worsen in severity, or AEs started prior to PS0018 dose, by PS0016 randomized treatment group

In addition, separate AE summaries by PS0018 dose at onset, SOC, HLT and PT will be included for the following AEs of special monitoring (AESM) further defined in [Section 14.3](#).

- Major cardiovascular events
- Serious infections, including opportunistic infections and tuberculosis (TB)
- Malignancies including lymphoma
- Cytopenias
- Neuropsychiatric events (in particular, depression and suicide)
- Inflammatory bowel disease
- Anaphylactic reaction (hypersensitivity and anaphylactic reactions)
- Hepatic events and drug-induced liver injury

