#### **14.3.5 Neuropsychiatric events**

This table is based on the SMQ of “Depression and suicide/self-injury” (all TEAEs that code to a PT included in the Scope=Broad and/or Scope=Narrow).

An external neuropsychiatric adjudication committee will evaluate potential neuropsychiatric events and determine whether any of those events were associated with suicidal ideation and behavior (SIB). If an event is adjudicated as SIB, further information will be provided. A separate listing for SIB events as determined by the adjudication committee will be included.

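### Anxiety is on the protocol's list of adverse events for special monitoring, but the SAP's neuropsychiatric search names only depression and suicide, and no change is declared

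*SAP*

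**What the plan says.** Protocol 9.6 gives a study-specific list of AESM. It opens "Adverse events for special monitoring for this study include: serious infections" and goes on to name suicidal ideation or behavior (assessed by C-SSRS) and, as a separate item, "depression and anxiety (assessed using the HADS", with a pointer to Protocol 12.4.

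The SAP carries the list forward in 11.2.3 and 14.3, where the psychiatric topic becomes "Neuropsychiatric events (in particular, depression and suicide". SAP 14.3.5 bases the table on one SMQ, "Depression and suicide/self-injury", and takes "all TEAEs that code to a PT included in the Scope=Broad and/or Scope=Narrow" of that query. The only other output in 14.3.5 concerns suicidal ideation and behavior (SIB): "A separate listing for SIB events as determined by the adjudication committee will be included".

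On what an AESM table contains, SAP 14.3 states: "All AESM tabulations will be presented by Treatment at onset, SOC, HLT and PT, based on the SS, and will include the EAIR and EAER", the two rates being limited to the Any TEAE rows. SAP 11.2.3 adds that the AE listing will flag AESM.

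SAP 3.9 declares three departures from the protocol: no physical examination summaries, LOCF in place of multiple imputation, and pooled adjuster groups. Anxiety is not mentioned.

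**The concern.** The search rule decides which events are marked as belonging to a monitored topic. The protocol names anxiety as a monitored topic, but the SAP contains no search that names it. An anxiety TEAE that does not happen to sit in the depression and suicide query would not be flagged as AESM. It would not enter any AESM subject count, and it would not contribute to an AESM EAIR or EAER in the 160mg, 320mg or all-bimekizumab columns.

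The primary safety variable is exposure-adjusted TEAE incidence, and a secondary objective is the safety of increasing the dose to 320mg Q4W. For a listed topic, a grouped rate by dose at onset is the output that speaks to both. Because the change is not declared, a reader of the study report could not tell whether anxiety was left out by decision or by oversight.

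**Working it through.** This is mainly a check of coverage, so the texts are set side by side first. The plan gives no figure to reproduce.

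**1. Is anxiety on the protocol list?** Yes, in Protocol 9.6, paired with depression and separate from suicidal ideation or behavior.

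**2. Does the SAP have a rule that names it?** No. The other Protocol 9.6 topics each have a definition in SAP 14.3:
- cardiovascular events: adjudication (14.3.1)
- infections: SOC, HLGT and a sponsor term list (14.3.2)
- malignancies: SMQs (14.3.3)
- cytopenias: SMQ (14.3.4)
- depression and suicide: SMQ (14.3.5)
- IBD: HLGT (14.3.6)
- hypersensitivity and anaphylaxis: term rule and algorithm (14.3.7)
- liver: SMQ and laboratory criteria (14.3.8, 14.2)

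Anxiety is the exception. Serious infections show that the SAP can be explicit about a lesser treatment: 14.3.2.1 defines them and says they get no table of their own. Nothing comparable is said for anxiety.

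**3. Where else does the SAP report anxiety?** In two places.
- *General TEAE tables (SAP 11.2.3).* Anxiety preferred terms would be counted by SOC, HLT and PT and by dose at onset. The rates are narrower: "Incidence of TEAEs by PS0018 dose at onset, including the EAIR and EAER calculated as described in" SAP 11.2.2, but for the Any TEAE category only. An individual anxiety term therefore has a count and no prespecified rate.
- *HADS-A (SAP 8.2.4).* This is a scale score treated as an efficacy variable on the FAS, by PS0016 randomized group and overall. It is not split by PS0018 dose at onset and is not an event rate. HADS is collected at Baseline and Weeks 12, 24, 36 and 48, and not at SFU.

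**4. How much of the TEAE window does HADS-A miss?** For a completer whose last dose is at Week 44:
- day of last dose: 44 × 7 = 308
- time at risk (SAP 11.1.2): 308 + 140 = 448 days
- last HADS: Week 48, day 48 × 7 = 336
- time after the last HADS: 448 − 336 = 112 days, and 112/448 = 25%

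**5. What is one omitted subject worth?** Assume that all 45 subjects (the protocol's upper limit) enrol, complete dosing and are followed for the full 140 days.
- subject-years at risk: 45 × 448/365.25 = 55.2
- incidence: 1/45 = 2.2 percentage points
- EAIR: 100 × 1/55.2 = 1.8 per 100 subject-years

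The last figure is approximate. Under SAP 11.2.2 time at risk stops at a subject's first event, so the true denominator is somewhat smaller. Early withdrawal, including the planned withdrawal of PASI50 failures, shortens it further. Either effect makes one subject count for more. The number of subjects affected is not given in the documents and is not estimated here.

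**The case against.** The strongest case against has four parts.

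*The protocol promises no such table.* Protocol 9.6 describes AESM as topics for monitoring, extra data collection or signal detection, and Protocol 14.2 plans no AESM tabulation. This stands: no protocol-specified analysis has been removed, and silence in SAP 3.9 is not in itself a breach. But the SAP chose to turn the protocol's list into search rules, flags and rates, and in doing so it left one listed topic without a rule.

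*The protocol names HADS as the tool for anxiety, and HADS-A is analysed.* This stands in part. Depression carries the same HADS note in the same phrase and still receives an AE-based table, so the note cannot explain why anxiety does not.

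*Anxiety events are still visible.* This stands. With at most 45 subjects, each anxiety term can be found in the general tables by dose at onset. What is missing is the grouped row, its rate and the AESM flag.

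*The query may catch some anxiety terms.* This cannot be excluded. The term list is not in the documents and 14.3.5 uses broad as well as narrow scope.

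Two stronger readings are tempting and should not be drawn. A reader might infer that the neuropsychiatric rate will be understated against the protocol's definition. The protocol defines no neuropsychiatric composite; it lists suicidal ideation or behavior separately from depression and anxiety, and the grouping exists only in the SAP. The table is not biased for what it says it counts. A reader might also infer that anxiety alone is denied an exposure-adjusted rate. SAP 11.2.3 limits EAIR and EAER to the Any TEAE category for every preferred term, so the lack of term-level rates is general. What is particular to anxiety is the missing AESM grouping that would have supplied one.

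**Conclusion.** The point holds as a gap between Protocol 9.6 and SAP 11.2.3, 14.3 and 14.3.5: a listed AESM has no search rule, and the SAP does not say that this is intended. Anxiety TEAEs outside the depression and suicide query lose the AESM flag, the grouped count, and the EAIR and EAER by dose at onset.

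The scale is modest. The per-subject values in the working rest on full enrolment and completion, and they illustrate leverage rather than predict an effect. The overall TEAE rate, the sample size and the data collected are unaffected, and there is no hypothesis test to distort. The extent of the omission depends on the query's contents, which the documents do not show. That uncertainty is itself a reason to fix a list in advance.

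**What to change.** In SAP 14.3.5, add a prespecified list of anxiety preferred terms or HLTs from MedDRA version 19.0, the version named in SAP 3.8. Report it as its own row with subject count, EAIR and EAER by PS0018 dose at onset. Leave the depression and suicide/self-injury row as it is, so that its meaning does not change. Flag the added events as AESM in the AE listing, and align the topic name in 11.2.3 and 14.3 with Protocol 9.6.

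If the sponsor instead intends HADS-A and the general TEAE tables to serve for anxiety, SAP 3.9 should say so and give the reason. That would reconcile the documents but would not supply the rate by dose.

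Either change belongs in a SAP amendment before database lock, as SAP Section 1 requires for modified definitions. The cost is one term list and one more row in a descriptive table, using AE data that are already collected and coded.

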#### 14.3.1 Major cardiovascular events

Major adverse cardiac events (MACE) will be presented in a table. The classification of an event as MACE is determined by an external cardiovascular event adjudication committee.

#### 14.3.2 Serious infections, including opportunistic infections and tuberculosis

##### 14.3.2.1 Serious infections

Serious infections are based on MedDRA classification using the SOC = 'Infections and Infestations'. Such events will be included in the tabulations of SAEs and no separate summary tabulations will be presented.

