All summary tables (including those for AESM) will contain the number and percentage of subjects and the number of events where applicable. A subject who has multiple events in the same SOC, HLT and PT will be counted only once in the subject counts but all events will be included. In addition, for all tabulations of AESM, the EAER and EAIR will be reported only for the categories 'Any TEAE'.

The criteria for identifying AESM and additional criteria for reporting AESM are provided in [Section 14.3](#).

Adverse event summaries will be ordered by alphabetical SOC, alphabetical HLT within SOC and decreasing frequency of PT in the 'BKZ 320mg' column for the PS0016 randomized treatment group. In the PS0018 dose at onset tables, the summaries will be presented in a similar manner in decreasing frequency of PT in the 'All BKZ' column.

For tables including only number and percentage of subjects, summaries will be ordered by alphabetical SOC, alphabetical HLT within SOC and decreasing incidence of PT within HLT and SOC in the 'All BKZ' column.

Any adverse events considered ongoing from PS0016 which do not worsen in severity during PS0018 dosing, or starting prior to first PS0018 dose will not be considered treatment emergent in PS0018 and will be tabulated separately.

The AEs will be listed by PS0016 randomized treatment group and include all subjects screened in the ES. The listing will include the onset date/time and outcome date/time of the event (including relative days), the AE duration (derived), dose at onset, days since first dose of study

medication, days since most recent dose of study medication, pattern of event, intensity, relationship, action taken and outcome. In addition the listing will flag AEs that led to discontinuation, TEAEs, AESM, AEs of special interest (as reported on the eCRF) and SAEs.

A glossary of all TEAE terms will be provided including the SOC, HLT, PT and reported term.

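### The SAP both promises and cancels a separate summary of serious infections; under the cancelling text, serious infections as a group have no exposure-adjusted rate

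*SAP*

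**What the plan says.** SAP 11.2.3 commits to "separate AE summaries by PS0018 dose at onset, SOC, HLT and PT will be included for the following AEs of special monitoring (AESM") and the list that follows contains "Serious infections, including opportunistic infections and tuberculosis (TB"). The same section settles the content of those tables: "for all tabulations of AESM, the EAER and EAIR will be reported only for the categories" of any TEAE, that is, for the overall row.

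SAP 14.3 repeats both commitments. It opens with "The following AESM are defined for bimekizumab and will be summarized separately as described in" SAP 11.2.3, and closes its list by saying that all AESM tabulations are by treatment at onset "and will include the EAIR and EAER in the" overall row.

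Two subsections later, SAP 14.3.2.1 defines serious infections through the MedDRA class for infections and infestations, places them in the SAE tables and says that "no separate summary tabulations will be presented".

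SAP 14.3.2.2 gives fungal infections a separate summary, and SAP 14.3.2.3 gives opportunistic infections, with tuberculosis, a stand-alone table. SAP 3.9, which lists departures from the protocol's analyses, does not mention serious infections.

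**The concern.** A programmer cannot satisfy both instructions. If SAP 14.3.2.1 is followed, the output drops the exposure-adjusted result for serious infections as a group.

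This matters because the primary safety variable in Protocol 4.1.1 is TEAE incidence adjusted for exposure, and Protocol 9.6 names serious infections as an event for special monitoring. The study is small and the event may be rare. With few or no events, the upper confidence limit of the rate is the most useful result, and a table of counts and percentages does not show it.

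Everyone starts on 160mg, and 320mg becomes available only from Week 12 for partial responders, so time at risk can differ between the dose columns. The documents do not allow the size of that difference to be stated in advance.

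**Working it through.** There is no stated figure to reproduce. The check has two parts: tracing where a rate for serious infections could appear, and showing what the missing rate would look like.

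**1. Tables that could carry the rate**

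| Table | Source | EAIR or EAER for serious infections as a group? |
|---|---|---|
| All TEAEs by dose at onset | SAP 11.2.3 | No. Rates are limited to the overall TEAE row, so the infections class row has none |
| Serious TEAEs by dose at onset and dose adjustment | SAP 11.2.3 | No. The entry names incidence only; the general rule gives subjects, percentages and event counts |
| Serious TEAEs by relationship | SAP 11.2.3 | No, for the same reason |
| Fungal infections | SAP 14.3.2.2 | No. A different group of events, serious or not |
| Opportunistic infections including TB | SAP 14.3.2.3 | Rates for that subset only, under the general rule in SAP 14.3 |
| Serious infections | SAP 14.3.2.1 | The table is cancelled |

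The other listed AESM (major cardiovascular events, malignancies, cytopenias, neuropsychiatric events, inflammatory bowel disease, hypersensitivity and anaphylaxis, hepatic events) all have a tabulation in SAP 14.3.

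**2. What the missing rate would look like**

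Inputs:
- at most 45 subjects (SAP 2.4);
- last dose at Week 44 (SAP 3.2.1.2);
- time at risk = last dose date − first dose date + 140 days (SAP 11.1.2, equation 15);
- 365.25 days per year (SAP 11.1.2);
- event counts, which are assumed.

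Maximum time at risk per subject: 44 × 7 + 140 = 448 days; 448 / 365.25 = 1.2266 years.

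Total over all doses: T = 45 × 1.2266 = 55.2 subject-years.

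SAP equation 17: EAIR = 100 × n / T.

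SAP equation 18, scaled by T: lower limit = 100 × χ²(0.025; 2n) / (2T); upper limit = 100 × χ²(0.975; 2(n+1)) / (2T).

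For n = 0 the upper limit is 100 × 3.689 / 55.2 = 6.68.

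| Subjects with a serious infection (assumed) | EAIR per 100 subject-years (95% CI), T = 55.2 | Same, if 70% of exposure accrues (assumed), T = 38.6 |
|---|---|---|
| 0 | 0 (0 to 6.68) | 0 (0 to 9.55) |
| 1 | 1.81 (0.05 to 10.09) | 2.59 (0.07 to 14.42) |
| 2 | 3.62 (0.44 to 13.09) | 5.18 (0.63 to 18.70) |
| 3 | 5.44 (1.12 to 15.88) | 7.76 (1.60 to 22.69) |

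SAP 11.2.2 stops a subject's time at the first event. The table ignores this; applying it would raise the nonzero rates slightly. The EAER has no interval for any event (SAP 11.2.2), so the only interval lost is that of the EAIR.

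**The case against.** The strongest reply is that SAP 11.2.3 refers the definition and reporting of AESM to SAP 14.3, so the event-level rule in 14.3.2.1 should override the general list, and the sentence on rates can be read as covering only the tables that exist. This gives a workable reading but does not remove the conflict. SAP 14.3 itself repeats that the listed AESM are summarized separately, every other listed AESM keeps a tabulation, and SAP 3.9 gives no reason for an exception.

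Several other replies stand and limit the point:

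- A reader might infer that this AESM is left with no exposure-adjusted result at all. It is not: opportunistic infections including TB keep a table that falls under the rule on rates.
- A reader might infer that serious infections go unreported by dose. They do not: the infections class row of the serious-TEAE table gives crude counts by dose at onset. Subject-years are listed and summed by dose (SAP 11.1.2), so an EAER could be worked out by hand, and an EAIR from the AE listing. The gap is in the planned presentation and its interval, not in the data.
- A reader might infer that the missing table would provide a fair comparison of doses. Subjects move to 320mg because of a partial response and at the investigator's discretion (Protocol 5.1), so a rate by dose is still confounded by that selection.
- Protocol 14.2.2 asks for a summary of serious TEAEs, which is kept, and the protocol does not ask for a serious-infection table by name. Protocol 14.2.1 did, however, plan the EAIR with its 95% interval in the TEAE summary by class and term. Once the SAP confines those rates to overall rows, the AESM tables are the only planned place for an event-specific rate.

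**Conclusion.** The contradiction is real and lies within the current SAP text. If SAP 14.3.2.1 is followed, serious infections as a group have no planned EAIR, no exact 95% interval for it, and no EAER. Crude counts remain, as does the table for opportunistic infections.

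The size can only be illustrated: 0 affected subjects would carry an upper limit of 6.7 per 100 subject-years, and 1 would give 1.8 (0.05 to 10.1). This assumes 45 subjects, all dosed through Week 44 and followed for the full 140 days, pooled over both doses; with less exposure the limits widen, as shown above. The documents do not support a claim about how far time at risk will differ between 160mg and 320mg, or about bias of a given size in the crude percentages. The point deserves correction because serious infection is a named monitoring event in a study whose primary variable is exposure-adjusted, and the correction is cheap.

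**What to change.** In SAP 14.3.2.1, delete the clause that rules out separate tabulations. Add one table of serious TEAEs in the infections and infestations class, by PS0018 dose at onset and for all bimekizumab, with EAIR, exact 95% interval and EAER in the overall row. Add a note that differences between dose columns are descriptive, because the move to 320mg depends on response.

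If the omission was intended, the lists in SAP 11.2.3 and 14.3 should be corrected and the reason recorded in SAP 3.9. That would remove the contradiction but leave the rate unreported, so adding the table is preferable.

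The cost is one extra table. The derivations already exist in SAP 11.1.2 and 11.2.2, and no further data collection is needed.
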